Recruitment of testing participants. Testing participants will be recruited in one of two ways: chain referral and credible messenger. In the chain referral strategy, an initial set of n=8 “seed” participants are recruitment by staff of eligible clients receiving services at Argus and Alliance (n=16 total seeds). For clinic-based recruitment of “seeds”, participants will be recruited from among those individuals who use opioids and other drugs who are receiving services through Argus or Alliance; services do not need to be substance use related. (Following a brief training, these “seed” participants then recruit additional participants (“peer recruits”) from among their own peer networks of those known to use opioid or other drugs in community settings (peer- recruitment). “Seed” participants are given three unique, numbered coupons, which they can give to people they know (peers) who are also use opioids and other drugs. The coupons will have information, by which peers who are interested in participating in the study can contact the research team to be screened for eligibility. Participants will receive renumeration for each peer recruit who enrolls in the study by redeeming a coupon given to them by that participant. Peer-recruits then repeat the same process with members of their peer network.

The credible messenger strategy involves leveraging the existing infrastructure at both Argus and Alliance, which includes credible messenger programs that are well-established, with considerable influence and impact within the respective communities served by these two agencies. The credible messengers within these programs have been trained to conduct community outreach to target individuals at increased risk for HIV, STIs, HCV and SUD and encourage testing and/or linkage to services. Interested credible messengers (n=4 from each site) will serve as messengers in the current study and will be trained to also include education about COVID-19, ways to reduce risk as well as ways to increase motivation to test for COVID-19 at the respective clinics. Credible messengers will conduct community outreach, targeting those locations and venues where potentially credible participants are located, and will provide education and encourage these individuals to seek testing. The potential participants will be given a coupon which will be redeemed at the clinic when the participant is enrolled in the study after being determined as eligible.

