As testing participants are assessed once and then offered a test immediately thereafter, study retention is not a considerable focus of procedures. Participants recruited by chain-referral will be given a brief survey following their recruitment efforts to document number of attempts, time etc. This brief survey will occur at the visit when the participant comes to the clinic to receive payment for redeemed coupons that s/he distributed to peers; it is anticipated the payment will serve to adequately retain participants for the purpose of completing the brief survey.

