
4.2. Sample Size Determination

Power calculations assume that we will be able to recruit 500 participants in total (250 recruited in each strategy) for this supplement study over Phases 2a and 2b. We also assume alpha (type I error rate) of 0.05. Our primary outcome of interest is testing occurrence. Based on zip-code level testing data, the average baseline testing in the communities of interest (i.e., northern Manhattan, the Bronx) is 7842.2/100,000. If we assume that one of the methods of recruitment will have a testing rate similar to this baseline average, we will have > 80% power to detect an approximately 8 percentage point difference in testing among the recruitment strategies (7.8% vs. 16.1%) corresponding to an odds ratio of 2.27, a moderate effect size.

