4.5 Statistical Analyses

4.5.1 Analysis overview and main outcomes. The primary outcome of interest comparing the strategies will be testing occurrence (yes vs. no) as an indicator of testing uptake. An important secondary outcome will be reach measured through the number of coupons redeemed. Prior to the main analysis, all variables will be examined for distribution and outliers. Continuous outcomes will be described through means and standard deviations, while dichotomous and categorical outcomes will be described through proportions.

4.5.2 Statistical analysis for Aim 2. Models that compare the effect of recruitment strategy on outcomes related to reach, testing uptake, and service delivery will adjust for measures assessed at baseline (e.g., baseline substance use, testing history). For our primary (dichotomous) outcome (testing uptake) logistic regression will be used: $\text{logit}(\text{pi}) = \beta_0 + \beta_{\text{RecStr}}(\text{Recruitment Strategy})_{ii} + \beta_{\text{Site}}(\text{Site})_{ii} + \beta_{\text{SubUse}}(\text{Substance Use})_{ii} + \beta_{\text{TestHis}}(\text{Testing History})$, thus be β_{RecStr} which will estimate the differential effect of chain-referral vs. POL recruitment on testing uptake. The model will be adapted for secondary outcomes. Sensitivity analyses will stratify the analyses by time to determine if recruitment strategy effects differed before and after the cross-over. Demographic characteristics and other variables related to the Andersen, SCT, and EPIS models will be examined as potential mediators/moderators.

4.5.3 Statistical analysis for Aim 3. Implementation features related to acceptability, sustainability, feasibility, and fidelity will be assessed at both the staff- and individual-level. As an illustrative example, we will consider whether participants endorse time constraints and the association with testing uptake. The logistic model will take the form $\text{logit}(\text{pi}) = \beta_0 + \beta_{\text{RecStr}}(\text{Recruitment Strategy})_{ii} + \beta_{\text{Site}}(\text{Site})_{ii} + \beta_{\text{TimeCon}}(\text{Time Constraint})_{ii}$ where pi is the probability of being tested post-recruitment for the i^{th} individual. This model assesses the effect of a time barrier on the likelihood of getting testing while controlling for the differing recruitment strategies and sites.

4.6. Subject participation duration:

N/A

4.7. FDA regulated intervention:

No

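### The primary logistic model and the power figure treat 500 recruits as independent, although they enter through 16 seed chains and 8 credible messengers

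*Combined protocol and SAP*

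**What the plan says.** **Model.** Section 4.5.2 says: "For our primary (dichotomous) outcome (testing uptake) logistic regression will be used". The linear predictor contains recruitment strategy, site, substance use and testing history, the baseline measures being given as examples. No random effect, GEE or cluster-robust variance is named. The one sensitivity analysis given for this model stratifies by time. Section 4.4.1 repeats the plain logistic form.

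**Power.** Section 4.2 takes 250 people per strategy and alpha 0.05, and concludes "we will have > 80% power to detect an approximately 8 percentage point difference in testing among the recruitment strategies (7.8% vs. 16.1"%). It mentions neither an ICC nor a design effect.

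**Recruitment.** Section 2.5 gives 8 seeds at each agency, 16 in all. Seed "participants are given three unique, numbered coupons, which they can give to people they know (peers"), and then: "Peer-recruits then repeat the same process with members of their peer network". In the other arm, "Interested credible messengers (n=4 from each site) will serve as messengers in the current study", so 8 in all, and "Credible messengers will conduct community outreach, targeting those locations and venues where potentially credible participants are located". For the messenger arm the text says only: "The potential participants will be given a coupon which will be redeemed at the clinic". Numbering of coupons is described for chain referral alone.

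**Timing of the test.** Section 2.5 begins its retention paragraph: "As testing participants are assessed once and then offered a test immediately thereafter". The description of test participant surveys in 3.1.1(b) likewise places testing at the end of the enrolment survey. No uptake rate among enrolled people is given.

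**The concern.** Everyone in a seed chain descends from one person through peer ties, and everyone brought in by one messenger shares that messenger and probably some venues. Because a whole chain or messenger belongs to one strategy, any within-recruiter correlation goes straight into the variance of the strategy contrast. A variance computed from 500 independent people then understates the uncertainty.

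The plan's own rationale makes positive correlation plausible: the Justification for Intervention argues that behaviour spreads along existing relationships. The argument is clearer for chains, which run through a person's own peers, than for messengers, who do venue outreach.

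The risk is that a difference among a few chains or messengers is reported as an effect of strategy. That comparison informs which strategy the agencies carry into Phase 3 and the scale-up described in 4.8.

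**Working it through.** **1. The stated power under independence.** Inputs from 4.2: p1 = 0.078, p2 = 0.161, n = 250 per strategy, alpha 0.05. Sidedness is not stated; two-sided reproduces the figure.

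- Pooled proportion 0.1195; SE0 = sqrt(2 × 0.1195 × 0.8805 / 250) = 0.02901.
- SE1 = sqrt(0.078 × 0.922/250 + 0.161 × 0.839/250) = 0.02877.
- Power = Φ[(0.083 − 1.96 × 0.02901)/0.02877] = Φ(0.908) = 81.8%.
- Odds ratio = (0.161/0.839)/(0.078/0.922) = 2.27, as stated.

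So the claim reproduces, on the basis of 500 independent people.

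**2. Design effects.** Mean cluster sizes are 250/16 = 15.6 (chains) and 250/8 = 31.25 (messengers). DE = 1 + (m − 1) × ICC. Equal cluster sizes are assumed, and ICC means the average pairwise correlation within a chain or messenger.

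**3. Type I error of the planned test.** With equal arms, the true variance under no effect is the naive variance times the mean DE, so error ≈ 2[1 − Φ(1.96/√mean DE)].

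**4. Power of a test that respects the clusters.** SE² = [pC(1 − pC)DE_C + pM(1 − pM)DE_M]/250, with C for chains and M for messengers. The reference is a noncentral t with 24 clusters − 4 parameters (intercept, strategy, site, period) = 20 df and critical value 2.086. The range covers either strategy having the lower rate. At ICC 0.02, for example, SE is 0.0352 or 0.0341, the noncentrality is 2.36 or 2.44, and power is 61.2% or 64.0%.

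| Assumed ICC | DE chains | DE messengers | Mean DE | Type I error (formula) | Power, 7.8% v 16.1% |
|---|---|---|---|---|---|
| 0 | 1.00 | 1.00 | 1.00 | 5.0% | 78% |
| 0.01 | 1.15 | 1.30 | 1.22 | 7.7% | 69-71% |
| 0.02 | 1.29 | 1.61 | 1.45 | 10.3% | 61-64% |
| 0.05 | 1.73 | 2.51 | 2.12 | 17.8% | 45-49% |

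**5. Simulation check of type I error.** This used beta-binomial outcomes, 40,000 trials per setting, and a logistic model with strategy and site and a Wald test. At ICC 0.01 / 0.02 / 0.05 the error was 7.6% / 10.0% / 17.7% at 12% uptake and 7.6% / 9.8% / 17.7% at 90%. With one assumed pattern of unequal cluster sizes and no site term, 17.6% at 90% uptake and ICC 0.05 became 24.8%.

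**6. Correlation in one arm only** (ICC 0.02 / 0.05, uptake 12% or 90%). Chains only: 6.5-6.6% / 9%. Messengers only: 8.1-8.4% / 13.5%. If chain correlation fades with each link, a mean of 0.015 or 0.05 across a 16-person, three-coupon tree needs a recruiter-recruit correlation of 0.10 or 0.25. The upper end is therefore less likely for chains.

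**7. Very high uptake.** Type I error at 98% uptake:

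| Test | ICC 0.01 | ICC 0.02 | ICC 0.05 |
|---|---|---|---|
| Wald | 3.1% | 4.4% | 8.5% |
| Likelihood ratio | 9.7% | 12.7% | 20.3% |
| Score | 7.1% | 9.6% | 16.3% |

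The Wald figure is low because that test is conservative with few untested people (1.8% at ICC 0), not because clustering has ceased to matter.

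**The case against.** **No ICC is documented.** True, and this is the strongest objection. Every size above is conditional. Substance use and testing history are in the planned model but not in the simulations, and they may absorb part of the correlation. A reader might infer that the strategy p-value is wrong by a known amount; the documents do not support that. They do show that zero correlation is assumed without being stated or defended.

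**Uptake may be near universal.** Since the test follows the enrolment survey directly, this is possible, and the 7.8% in 4.2 is a zip-code community rate that may not describe enrolled people. A reader might infer that high uptake makes the problem vanish. It does not in general: at 98% the Wald test stays at or below 5% only for ICC up to about 0.02, the likelihood-ratio and score tests stay inflated, and 4.5.2 does not say which test is used.

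**The comparison may not settle Phase 3.** A reader might infer that this p-value decides which strategy is carried forward. The Phase 3 description speaks of outcomes in the plural, and Table 5 also types reach, service delivery, acceptability and sustainability, feasibility and fidelity as primary. The documents support only that the comparison informs the choice.

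**Enrolment is over.** Section 2.6 says the study is not recruiting and Table 1 lists 486 participants, so a new power figure is disclosure only. The analysis can still be corrected; the documents do not say whether it has been run.

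**Conclusion.** The point stands as an omission with conditional consequences. Neither 4.5.2 nor 4.2 allows for recruitment through 24 chains and messengers, and no other section does so. If outcomes are positively correlated within recruiter, the planned p-value is too small and the interval too narrow. At an assumed ICC of 0.01 to 0.05 in both arms, the true error of a 5% test is about 8% to 18% at 12% or 90% uptake. Power falls from the claimed figure to between 71% and 45%; even at ICC 0, a test with 20 df gives 78%. With 486 enrolled (243 per strategy assumed, since the split is not given), the powers are 77% at ICC 0 and 68-70% / 60-63% / 45-49% at ICC 0.01 / 0.02 / 0.05.

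Confidence is high that the adjustment is missing, and much lower about how large the correlation is. The figures rest on assumed ICCs, equal cluster sizes, a two-sided test and no baseline covariates. The stated power should not be used to interpret a null result.

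**What to change.** **Section 4.5.2.**
- Keep the planned covariates and use cluster-aware inference, with the root seed or individual messenger as the cluster: GEE with robust variance, or a random intercept, with a small-sample correction for about 24 clusters.
- Fix one sparse-data rule in advance. If any clinic-period cell has nobody untested, or overall uptake exceeds one stated cut-off no higher than 90%, use a size-weighted comparison of cluster proportions adjusted for site and period (t, 20 df). State that substance use and testing history are then not adjusted for. Alternatively, make that comparison primary throughout.
- The rule is needed because the simulated error of the logistic GEE was 4.8-6.3% for uptake of 7.8% to 90%, but reached 10.9% at 95% and 27-47% at 98%. The cluster-proportion test held 4.5-5.9% from 12% to 98%.
- If the planned analysis has been run, report the cluster-aware result beside it.

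**Data.** The numbered coupons should identify the root seed. Confirm that messenger coupons can be traced to the messenger. If they cannot, report messenger clustering as an unadjusted limitation with an ICC range.

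**Section 4.2.** Replace the single power figure with power over a stated ICC range for the test actually used, as disclosure only.

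**Limitation to state.** With two clinics and one switch, strategy is an unreplicated site-by-period contrast, and this fix does not remove clinic-period variation. At a recruiter ICC of 0.02, 12% uptake and an assumed clinic-period ICC of 0.005 / 0.01 / 0.02, the cluster-aware tests still have type I error of about 10% / 15% / 21-24%.

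**Secondary and separate.** Add a period term beside site. It matters only if the sites enrol unequally across periods and uptake shifts. With an assumed 60:40 or 70:30 site split and an 8-10 point shift, the planned model's error is about 8-9% or 15-23%, and about 5% with period included.

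**Cost.** SAP wording, a changed variance estimator, one model term, and possibly recovery of messenger identifiers from recruitment records. Intervals will be wider, and power is about 3-4 points below the stated test even at ICC 0 (81.8% to 78.3%).

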- **Phase 2: Efficacy Test and Implementation Evaluation**, a trial will be performed in which the two strategies will be compared with respect to reach, testing uptake and related services; we will aim to recruit 500 participants who use opioids or other substances over an 8 month period of time (n=250 in each strategy). Participants will be assessed upon enrollment into the study. In addition, n=8 credible messengers (n=4 at each site), and n=20 staff members at each site employed at our community partners agencies Alliance and Argus, will complete baseline and 12-month follow-up surveys, fidelity/feasibility checklists, PDSA cycle and will participate in a workgroup at the completion of Phase 2.
- **Phase 3: Sustainment**, CBOs will implement the strategy proven efficacious based on outcomes, and we will examine their sustainment of the program.

- The **two recruitment strategies** used in Phase 2 are **chain referral** and **credible messenger**:
 - 1) In the **chain referral strategy**, an initial set of n=8 “seed” participants are recruitment by staff of eligible clients receiving services at Argus and Alliance (n=16 total seeds). For clinic-based recruitment of “seeds”, participants will be recruited from among those individuals who use opioids and other drugs who are receiving services through Argus or Alliance; services do not need to be substance use related. (Following a brief training, these “seed” participants then recruit additional participants (“peer recruits”) from among their own peer networks of those known to use opioid or other drugs in community settings (peer-recruitment). “Seed” participants are given three unique, numbered coupons, which they can give to people they know (peers) who are also use opioids and other drugs. The coupons will have information, by which peers who are interested in participating in the study can contact the research team to be screened for eligibility. Participants will receive renumeration for each peer recruit who enrolls in the study by redeeming a coupon given to them by that participant. Peer-recruits then repeat the same process with members of their peer network.

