Social network strategies effective at identifying hidden populations and improving access to HIV related services may improve uptake of COVID-19 testing. Social network interventions utilize existing patterns of relationships to accelerate behavior change have been successful in increasing the uptake of HIV testing among marginalized populations, including people who use drugs. Moreover, social network approaches successfully counter stigma, medical mistrust, and misinformation around HIV, making them uniquely suited for addressing similar issues in the context of COVID-19. Two distinct social network recruitment strategies, chain-referral and Popular Opinion Leader (POL or “credible messenger”) models may be promising for increasing rapid COVID-19 testing. In chain-referral a discrete number of “seeds” are identified and incentivized to refer members of their social networks, who in-turn repeat the process. In POL models, popular and socially influential individuals with lived experience are trained to engage within formal and informal social networks to promote behavior change. Based on the efficacy of chain-referral and POL recruitment in the context of the HIV/AIDS epidemic, the success of these strategies to promote COVID-19 testing in underserved populations of substance users is highly plausible. Given the distinct differences of these strategies, it is important to contrast them to determine the comparative benefits of one approach over the other.

Ongoing quality improvement (QI) to promote an adaptive response to an evolving epidemic and promote sustainability. Plan-do-study-act (PDSA) is an evidence-based, rapid-cycle change model for testing enhancements on a small scale before incorporating them on a larger scale. Training staff, and POLs to use data (e.g. testing uptake, client feedback) to monitor and improve program performance may be a useful tool to develop sustainable strategies that address a rapidly changing pandemic as well as incorporate new testing, treatment and prevention (i.e., vaccine) technology.

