We propose research to establish efficacy and sustainability of a community-social network outreach model that partners infectious disease health providers with community based organizations to successfully implement (reach, uptake, delivery and sustainment) COVID-19 rapid POS testing among a highly vulnerable and often underserved population, those who use opioids and other substances. Two distinct social network recruitment strategies, found efficacious for identifying HIV+/high risk populations and increasing uptake of HIV testing (cites) will be adapted and compared. Guided by the EPIS framework, SCT, and Andersen's model, this 2-year study will comprise three phases. In Phase 1: Adaptation of outreach recruitment strategies, we will work with our project CAB, via a CBPR approach, to adapt chain-referral and credible messenger strategies for uptake of COVID-19 testing, to finalize recruitment and on-site testing protocols, and to train the CAB in the new protocols and in continuous quality improvement strategies (Aim 1). In Phase 2: Strategy Efficacy Trial and Implementation Evaluation, we will compare the two strategies in a cross-over design at two CBOs, with initial strategy assignment randomly determined and rolled out for 4 months before the cross-over occurs. The comparison of chain-referral and credible messenger strategies is not to identify the statistical superiority of one sampling strategy in providing population estimates over the other, but instead to identify the ability of each recruitment strategy to reach the target population and increase uptake of COVID-19 tests. We will examine the impact of each strategy on (i) reach (recruitment of target population), (ii) COVID-19 testing/repeat testing, and (iii) service delivery (i.e. quarantine, medical care and contact tracing) among those who test positive for COVID-19 (exploratory) (Aim 2). In Phase 3: Sustainment, CBOs will implement the strategy proven efficacious based on outcomes, and we will examine their sustainment of the program (Aim 2). Implementation evaluation will identify participant-, staff-, and organizational-level factors that influence the feasibility, acceptability, and sustainability of each strategy in these CBOs. Participants will be assessed just prior to receipt of testing. Argus and Alliance staff will be assessed before and after the roll-out of strategies (Aim 3).

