We will examine the impact of the intervention on (i) reach, (ii) testing uptake and (iii) service delivery (i.e. quarantine, medical care and contact tracing among COVID-19 positive cases); and (iv) sustainability for individuals who use opioids and other drugs as well as potential mediating/moderating variables from the Andersen, SCT and EPIS models. Data drawn from Healthix on prior and future COVID-19 testing will augment study data to determine access to underserved populations and influence on future testing behavior. RAs will conduct interviews in private rooms at Argus and Alliance. Participants will be assured that responses are confidential (see Human Subjects). Interviewers will be trained with established protocols, covering informed consent, confidentiality, reporting requirements, interview content, and cultural sensitivity.

End-of-Study Definition

This study will be stopped prior to its completion if: (1) the intervention is associated with adverse effects that call into question the safety of the intervention such as increased rates of COVID-19 infection; (2) difficulty in study recruitment or retention, or enrollment of participants will significantly impact the ability to evaluate the study endpoints; (3) any new information becomes available during the trial that necessitates stopping the trial; or (4) other situations occur that might warrant stopping the trial.

Human Subjects Characteristics

Setting. Participants will be recruited from Washington Heights, Harlem two neighborhoods in northern Manhattan, the Lower East Side, a neighborhood in southern Manhattan, and the South Bronx, the locations and geographic catchment areas of Argus and Alliance. In addition to current demographics of their current

substance using clientele, we anticipate participants will comprise 64% male, 51% African American, 39% Hispanic.

Randomization. Just prior to the onset of Phase 2, the chain referral strategy will be randomly assigned (50:50) to a clinic in order to begin the first roll out. After the initial roll out and plan-do-study-act cycle (PDSA), the assignment will be switched such that the chain referral is then implemented at the other site.

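### With two clinics that swap strategies, the time-stratified analysis cannot separate strategy from clinic, and the primary model has no period term

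*Combined protocol and SAP*

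**What the plan says.** Section 3.1.1(a), under Justification for Intervention, sets out to "compare the two strategies in a cross-over design at two CBOs, with initial strategy assignment randomly determined and rolled out for 4 months" before the switch. Under Randomization in the same section, "the chain referral strategy will be randomly assigned (50:50) to a clinic in order to begin the first roll out"; after that roll-out and a plan-do-study-act (PDSA) cycle, "the assignment will be switched such that the chain referral is then implemented at the other site". Each clinic therefore runs one strategy per period.

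Recruitment targets are given per strategy. Phase 2 aims for 500 participants "over an 8 month period of time (n=250 in each strategy"), and Section 4.2 assumes "500 participants in total (250 recruited in each strategy) for this supplement study over Phases 2a and 2b". No target per clinic or per period appears in the text that could be read; the timeline in Figure 1 could not be.

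Section 4.5.2 writes the primary logistic model with four terms: strategy, site, substance use and testing history. Time enters only through a further sentence: "Sensitivity analyses will stratify the analyses by time to determine if recruitment strategy effects differed before and after the cross-over".

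**The concern.** There are two linked problems.

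First, stratifying a two-clinic, two-period cross-over by period leaves one clinic per strategy in each stratum. A lasting difference between the clinics, for instance in catchment or clientele, would appear as a strategy effect that changes at the cross-over. Where the true strategy effect is smaller than the clinic difference, it would appear to reverse.

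Second, the usual protection of a cross-over against calendar change is a period term, and the primary model has none. Such change is expected here: Section 3.1.1(a) describes quality-improvement training as a means to sustain "strategies that address a rapidly changing pandemic as well as incorporate new testing", and a PDSA cycle falls between the two roll-outs. If the strategies are spread differently over the two periods, change common to both clinics enters the strategy coefficient.

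At stake is which strategy is carried into Phase 3 and recommended for scale-up.

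**Working it through.** **The plan's own figure.** Section 4.2 gives 7.8% vs 16.1%, 250 per strategy, alpha 0.05. Odds ratio = (0.161/0.839)/(0.078/0.922) = 2.27, as stated. Two-sided power is 81.8% (pooled-variance test of proportions) or 80.1% (Wald test on the log odds ratio), so the claim of more than 80% reproduces. It does not bear on the two problems, but it supplies the rates used below.

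**Identifiability (no assumed rates).** The four cells are: clinic A period 1 chain; clinic B period 1 messenger; clinic A period 2 messenger; clinic B period 2 chain.

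- Intercept + strategy + site within one period: 3 columns, rank 2. Not estimable.
- Intercept + strategy + site over all four cells: rank 3 of 3. Estimable.
- Adding period: rank 4 of 4. Estimable, but the four cells are then saturated.
- Adding strategy-by-period, or instead site-by-period: 5 columns, rank 4. Not estimable.

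Write logit(p) = a + σ·(clinic B) + γ·(chain). The chain-vs-messenger log odds ratio is γ − σ in period 1 and γ + σ in period 2. The before/after difference is 2σ, which is twice the clinic difference and says nothing about change in γ.

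**Size of the stratified artefact.** Assume no strategy effect, 125 per cell, and one clinic at 7.8%.

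| Other clinic | Odds ratio in the two strata | Strategy-by-period test without site rejects |
|---|---|---|
| 10% | 1.31 and 0.76 | 13.8% |
| 12% | 1.61 and 0.62 | 34.5% |
| 16.1% | 2.27 and 0.44 | 80.1% |

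Check at 12%: difference = 2·ln(1.612) = 0.955; SE = √[2/(125·0.12·0.88) + 2/(125·0.078·0.922)] = 0.612; z = 1.56; Φ(1.56 − 1.96) ≈ 0.345.

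**Omitted period term.** Let c₁ and m₁ be the period 1 numbers on chain and messenger. With 250 per strategy, clinic A's total is c₁ + (250 − m₁), so the two splits match exactly when each clinic totals 250. Assume no strategy effect, period 1 at 7.8% in both clinics, and a common period 2 rate. A logistic model with strategy and site was fitted to expected counts. False positives = Φ(z − 1.96) + Φ(−z − 1.96), with z = coefficient/SE. Entries are odds ratio (false-positive rate).

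| Chain P1/P2 | Messenger P1/P2 | Clinic totals | P2 16.1% | P2 12% | P2 10% |
|---|---|---|---|---|---|
| 125/125 | 125/125 | 250/250 | 1.00 (5%) | 1.00 (5%) | 1.00 (5%) |
| 50/200 | 50/200 | 250/250 | 1.00 (5%) | 1.00 (5%) | 1.00 (5%) |
| 100/150 | 125/125 | 225/275 | 1.08 (6%) | 1.05 (5%) | 1.03 (5%) |
| 75/175 | 125/125 | 200/300 | 1.18 (9%) | 1.10 (6%) | 1.06 (5%) |
| 50/200 | 125/125 | 175/325 | 1.31 (16%) | 1.18 (8%) | 1.10 (6%) |
| 50/200 | 175/75 | 125/375 | 1.49 (30%) | 1.27 (12%) | 1.15 (7%) |

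Hand check of the third row at 16.1%, ignoring site: chain (100·7.8 + 150·16.1)/250 = 12.78%; messenger (7.8 + 16.1)/2 = 11.95%; odds ratio = (0.1278/0.8722)/(0.1195/0.8805) = 1.08. For the last row at 12%: coefficient 0.238, SE 0.300, z = 0.79, giving 12%.

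With a period term every entry is 1.00. Swapping which strategy is weighted to the later period reverses the direction.

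**What a period term leaves in.** With equal cells, if only the clinic running chain referral second rises from 7.8% to 10%, 12% or 16.1%, the odds ratio with the period term is still 1.15, 1.27 or 1.51 (false positives 7%, 12%, 26%).

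**The case against.** The stratified analysis is only a sensitivity analysis. The pooled primary model contains site and does identify strategy. That is right, and it is why the main comparison is not aliased with clinic.

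A reversal appears only when the strategy effect is smaller than the clinic difference. At the planned odds ratio of 2.27, clinic odds ratios of 1.31 or 1.61 give strata of 2.97 and 1.73 (2.27 × and ÷ 1.31) or 3.65 and 1.41 (2.27 × and ÷ 1.61): different sizes, same direction. That stands as a limit on how misleading the output would be. It does not let the analysis answer its question.

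The bias from omitting period is conditional, and the large figures need severe imbalance together with a doubling of testing. Of the twelve unbalanced scenarios, six have false-positive rates of about 6% or less. The plan also gives each clinic equal recruiting resources: 8 seeds, 4 credible messengers, and four months before the switch. This makes gross imbalance less likely, but these are not enrolment limits and they do not fix clinic totals.

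The 7.8% is a zip-code testing rate. Sections 2.5 and 3.1.1(b) have participants offered or given a test right after the survey, so uptake among those enrolled could be far higher. The sizes above would then change; the aliasing and the condition for bias would not.

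Finally, the baseline covariates in 4.5.2 are given as examples. But the formula is written out without period, and period is not a baseline measure. Phase 3 is also to be decided on outcomes in general, not testing uptake alone.

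**Conclusion.** Both parts hold. The stratified analysis cannot deliver its stated purpose; that rests only on the design in Section 3.1.1(a) and needs no assumed rate. The missing period term is a conditional weakness: no bias when clinic totals are equal, little when imbalance or calendar change is modest (odds ratio 1.03 to 1.08 at totals of 225/275), and substantial only when both are large (1.49, 30% false positives, at 125/375). All rates and splits are assumptions. Participants are treated as independent despite peer recruitment, and substance use and testing history are left out of the calculations. The point should be fixed. It does not invalidate the trial, but it affects how the strategy comparison can be read.

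**What to change.** In Section 4.5.2:

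1. Add a roll-out period term (first/second) to the primary model and to the models adapted for secondary outcomes. For service delivery, which is exploratory and confined to positive tests, the data may be too sparse for another term; the four-cell counts can then be reported instead.
2. Replace the stratified strategy-effect analysis with a descriptive clinic-by-period table of numbers enrolled and tested, or keep the stratum contrasts and label them as strategy plus site.
3. State that this design cannot separate a change in strategy effect over time from site, or a clinic-specific calendar change from strategy, so the period term removes only change common to both clinics.

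The covariate is already known for everyone. Section 2.6 lists the study as not recruiting and Table 1 shows 486 enrolled, but no new data are needed.

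The cost is precision. With period rates of 7.8% and 16.1%, the SE of the strategy coefficient rises as follows:

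| Chain vs messenger split | SE without period | SE with period | Increase |
|---|---|---|---|
| 125/125 vs 125/125 | 0.276 | 0.292 | 6% |
| 100/150 vs 125/125 | 0.273 | 0.300 | 10% |
| 75/175 vs 125/125 | 0.274 | 0.316 | 15% |
| 50/200 vs 125/125 | 0.280 | 0.348 | 24% |
| 50/200 vs 175/75 | 0.277 | 0.351 | 27% |

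The term can cost precision even where there is no bias to remove: at 50/200 in both strategies the SE goes from 0.318 to 0.397. At the planned effect with no period change, power stays at about 80% with equal cells. It falls from about 76% to 73% at 50/200 vs 125/125, and from about 80% to 69% at 50/200 vs 175/75.
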